clinical information to families and non-expert clinicians. In collaboration with the biomarker clinical research study, this study will also aid in biomarker development and correlation with clinical features. The following rationale for this research underscores its significance for CDG.

More than half of human proteins are glycosylated.¹ The glycome defined as the sugar chains (glycans) that an organism makes, is $\sim 10^2$ – 10^4 times larger than the proteome.² Given this complexity, it is not surprising that about 2% of our genes encode for proteins known to participate in glycosylation reactions.^{2,3}

A congenital disorder of glycosylation is a monogenic disorder in which proper modification of an organic molecule with a sugar or sugar structure is disrupted. PMM2-CDG, the first CDG that was clinically described in 1980 had its underlying genetic and enzymatic defect determined in the mid-late 1990s. The field has been expanding rapidly with the advent of genomic sequencing, with many novel CDG identified in the last few years.³ Although ~ 130 genetic disorders are associated with a dysfunction of one of these proteins, CDG are rare both individually and as a group. The most common type of CDG involves N-glycosylation defects (Figure 1).

[figure not shown]

Figure 1: Overview of N-glycosylation, a step-by-step process. Any defect in these steps could lead to a CDG. (The sugars are depicted with standard colored symbols).

Worldwide, **PMM2-CDG (CDG-Ia)** remains the most common CDG with ~ 900 cases reported.³ PMM2-CDG prevalence may be as high as 1 in 20,000 individuals in some populations.⁴ The next most common subtype is ALG6-CDG (CDG-Ic), with 50 cases⁵. **Congenital disorders of galactosylation are one of the largest subgroup**, including more than 70 reported cases of PGM1-CDG and SLC35A2-CDG(Radenkovic, in press). PMM2-CDG and galactosylation defects are typically detectable in blood and show an abnormal N-glycan pattern.

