Since so many biologic functions depend upon correct protein and lipid glycosylation, clinical CDG manifestations are widely variable within and among subtypes and across the lifespan. The clinical findings in affected individuals reflect glycosylation's role in the embryology and biology of many organ systems. Clinical findings may include developmental delay/intellectual disability with abnormalities in brain MRI, hypotonia, failure to thrive or growth impairment, hepatopathy, coagulopathy, immunodeficiency, protein losing enteropathy, osteopenia, skeletal dysplasias, renal abnormalities, functional and/or anatomic eye involvement, endocrinopathies, and peripheral neuropathy. Some CDG present with only tissue-specific symptoms such as SEC23B-dyserythropoietic anemia or Leukocyte Adhesion Deficiency Type II.⁶

Of the known 137 glycan-synthesis disorders we have potential therapies for only 8 disorders and not all current therapies are fully effective. Clinical trials have not validated these treatments for safety and efficacy. MPI-CDG has been treated with oral mannose.⁷ In SLC35C1-CDG, some patients respond to oral fucose supplementation. This treatment is only effective for the typical recurrent infections with hyperleukocytosis and does not correct the neurological issues of these patients.⁶ PIGM-CDG, the mutation described in the only published case so far, causes histone hypoacetylation at the PIGM promoter. Butyrate controls the seizures.⁸ PGM1, a critical enzyme for the

conversion of glucose-1-phosphate to glucose-6-phosphate, is at the crossroads of the glycogen, glucose and galactose pathway. **PGM1 deficiency is treatable with D-galactose**, alleviating the hypoglycemia, coagulopathy, and endocrinopathy seen in this disorder,^{9,10} although not the cardiomyopathy. The glycosylation defect CAD-CDG has been treated with uridine.^{11,12} Magnesium can improve MAGT1-CDG. Manganese and D-galactose have been used to treat TMEM165-CDG, whereas **SLC35A2-CDG has been treated with D-galactose**. From the group of disorders of de-glycosylation preclinical trials suggested positive effect of **GlcNAc treatment in NGLY1** deficiency.

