Given the rarity and novelty of CDG, the geographic spread of affected individuals, the broad clinical spectrum, the limited retrospective attempts at natural history studies (focused on one disorder or limited to one site), there is a significant **knowledge gap** regarding the progression and clinical variation in this group of disorders. Even for PMM2-CDG, preliminary data from an unpublished study emphasized that there is a need for prospective natural history studies to validate and expand on retrospective, limited results. This gap impedes the development of novel targeted therapeutics since there is no clear outcome measure for clinical trials, and it will be difficult to determine efficacy of a therapy over natural history.

Study Design and Methods

Methods:

Enrollment:

We will recruit and enroll patients with CDG in this study evaluating clinical variation and natural history when a patient is being seen as part of routine clinical care. We will invite eligible subjects to participate in the study to consent, enroll, and collect baseline data. We may also send consent forms in the mail to participants to consent or reconsent. All subjects for this study will be provided a consent form describing this study and providing sufficient information for subjects to make an informed decision about their participation in this study. This consent form will be submitted with the protocol for review and approval by the IRB for the study. The formal consent of a subject, using the IRB-approved consent form, must be obtained before that subject undergoes any study procedure. The consent form must be signed by the subject or legally acceptable surrogate, and the Investigator designated research professional obtaining the consent.

Study Activities:

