Inclusion Criteria: All individuals with a genetically, enzymatically, or molecularly confirmed diagnosis of CDG or NGLY1 deficiency, or individuals whose laboratory values are highly suggestive of CDG, but who do not have a verifiable diagnosis possibly due to difficulty with clinical molecular testing will be invited to enroll. Or those without confirmatory testing, they will be enrolled as "CDG highly likely/diagnosis pending" if the site PI and study PI concur. These individuals should have their diagnosis confirmed within one year of enrollment. If not confirmed they will be removed from the study. The study requires a minimum number of 50 patients with the diagnosis PMM2-CDG.

Exclusion Criteria: none

Biospecimens

Collection of blood samples.

- a. **From healthy, non-pregnant, adult subjects who weigh at least 110 pounds.** For a minimal risk application, the amount of blood drawn from these subjects may not exceed 550ml in an 8 week period and collection may not occur more frequently than 2 times per week.
Volume per blood draw: 30ml
Frequency of blood draw (e.g. single draw, time(s) per week, per year, etc.) annually (up to 5 visits)
- b. **From other adults and children considering age, weight, and health of subject.** For a minimal risk application, the amount of blood drawn from these subjects may not exceed the lesser of 50 ml or 3 ml per kg in an 8 week period, and collection may not occur more frequently than 2 times per week.
Volume per blood draw: up to 30 ml max, will draw minimum amounts not to exceed 3 mls/kg of weight. This will be calculated for each pediatric patient
Frequency of blood draw (e.g. single draw, time(s) per week, per year, etc.) annually (up to 5 visits)

Prospective collection of biological specimens other than blood: random urine, random stool at each annual visit (once per year over 5 year follow up)

Review of medical records, images, specimens

Check all that apply (data includes medical records, images, specimens).

Only data that exists before the IRB submission date will be collected.

Date Range for Specimens and/or Review of Medical Records:

Examples: 01/01/1999 through 12/31/2015, or all records through mm/dd/yyyy.

Note: The Date Range must include the period for collection of baseline data, as well as follow up data, if applicable.

The study involves data that exist at the time of IRB submission **and** data that will be generated after IRB submission. Include this activity in the Methods section.

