With the data collected over time, the average trend with age will be estimated using mixed effects models to account for the correlation of repeated measures from a subject. The model will include fixed and random effects for the intercept and slope (age). Maximum likelihood estimates (MLE) will be obtained for regression coefficients for fixed effects and restricted MLE for the variance component. The association of a factor of interest with a response variable will be examined using mixed effects models to account for the subject specific change. For a time constant factor, the model will include the factor, age and an interaction term between the factor and age as fixed effects. The model will also include random effects for the intercept and slope (time). For a time varying factor, the model may include baseline value of the factor and the change at the next visit as fixed effects to estimate cross-sectional and longitudinal effects simultaneously.

We will compare results of PROs to NPCRS subdomain scores, physical exam findings, and laboratory findings that should be reflected in that tool to assess the validity of each PRO measure. Partial least squares (PLS) regression analysis will be utilized to identify patterns of association between the PROs and the clinical scores. The PLS analysis and significant weights may reveal novel composite scores for CDG patients. Changes in PRO scores over time will be tested for association with Quality of Life questions using random effects generalized linear regression models incorporating a random intercept for each participant. We will also compare subsequent scores on the PROs from the same subject to determine reliability of the PRO if there has been no significant interval change in the clinical status. Reliability will be assessed by the weighted Kappa to account for the ordinal variables.

Expected Outcomes.

References:

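### For CDG types with a therapy, the age-trend model mixes treated and untreated visits, and the plan should report them separately before presenting the result as natural history

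*Combined protocol and SAP*

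**What the plan says.** The stated objective (Research Question and Aims) is to define the natural history of CDG. The end of the Background explains the need: without such data, "it will be difficult to determine efficacy of a therapy over natural history".

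Under Data Analysis Plan, "the average trend with age will be estimated using mixed effects models". The sentence that follows limits the terms to an intercept and an age slope, each fixed and random. Neither treatment nor CDG type is among them.

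The same section then gives generic models for a factor of interest: "For a time constant factor, the model will include the factor, age and an interaction term between the factor and age as fixed effects". For a time-varying factor the wording is permissive, and treatment is not named. Adjustment for unnamed confounders is mentioned only for the baseline associations.

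The Background describes therapies for eight synthesis disorders. It states, for example, that "PGM1 deficiency is treatable with D-galactose", with benefit for glucose control, clotting and endocrine function but not for the heart muscle. It also says that trials have not validated these therapies and that not all are fully effective.

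The Subject Information section reads "Exclusion Criteria: none", and Accrual plans 150 patients from all CDG types, at least 50 of them with PMM2-CDG.

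**The concern.** A patient already on therapy, one who starts it during follow-up and one who joins an interventional trial all contribute every visit to the same age trend. For a CDG type with a therapy, the fitted line therefore describes neither the untreated course nor the treated course.

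This matters because the Background presents natural history as the yardstick for future therapies. If therapy slows progression, a blended line can make a new therapy look less effective than it is. Improvement after a patient starts therapy during follow-up would be absorbed into the age slope and could pass for spontaneous change. Aim 1 also estimates organ involvement, and the Background counts clotting and endocrine problems both among CDG findings and among the features that galactose improves in PGM1-CDG. For such features, prevalence in treated patients describes disease under care.

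**Working it through.** **Step 1. How many types are affected.** The Background names MPI, SLC35C1, PIGM, PGM1, CAD, MAGT1, TMEM165 and SLC35A2. That is eight, which agrees with its own count of 8 out of 137: 8/137 = 5.8% of types. NGLY1 deficiency is mentioned in addition, with preclinical support only. No therapy is listed for PMM2-CDG.

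**Step 2. What share of patients this could be.** The documents do not say, so the following are scenarios. At most 100 of the 150 patients can have a type other than PMM2-CDG.
- Low: 5.8% of those 100 have a treatable type. 100 × 0.058 / 150 = 3.9% of the cohort.
- High: the Background describes the galactosylation group as "including more than 70 reported cases of PGM1-CDG and SLC35A2-CDG" and gives 50 cases of ALG6-CDG. Using those counts alone, 70/(70 + 50) = 58.3%, and 100 × 0.583 / 150 = 38.9% of the cohort.

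Having a treatable type is not the same as being treated, so each figure is a ceiling within its scenario.

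**Step 3. Effect on the pooled slope.** Let f be the treated share, r the fraction of progression that therapy removes, and k the slope that treated patients would have had without therapy, relative to the slope of untreated patients. With treatment status constant over follow-up:

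all-visits slope / slope of untreated patients = (1 − f) + f × k × (1 − r)

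If k = 1, this reduces to 1 − f × r, so the attenuation is f × r:

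| f (assumed) | r = 25% | r = 50% | r = 100% |
|---|---|---|---|
| 3.9% | 1.0% | 1.9% | 3.9% |
| 20% | 5.0% | 10.0% | 20.0% |
| 38.9% | 9.7% | 19.4% | 38.9% |

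The r = 100% column is a bound; the Background itself says that not all therapies are fully effective.

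**Step 4. Within one treatable type.** If 50% to 80% of its patients are treated and therapy removes 50% to 100% of progression (both assumed, k = 1), the slope is 1 − 0.5 × 0.5 = 75% down to 1 − 0.8 × 1.0 = 20% of the untreated slope.

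**Step 5. Why the direction is not settled.** If patients with faster progression are treated first, k exceeds 1. The all-visits slope equals that of untreated patients when k = 1/(1 − r), which is 2 at r = 50%, and is steeper beyond that. Measured against the course that the whole type would have had without therapy, the all-visits slope is too shallow for any r above 0. The documents give no value for r or k.

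**The case against.** The strongest reply is that therapy is a marginal matter here. Only 8 of 137 disorders have even a potential therapy, none is validated, and the PIGM example rests on a single published case. The reported PGM1 and SLC35A2 cases are not cohort members, and no document counts treated participants. This stands against a reading that many of the enrolled types are on therapy, which the documents do not support. It does not remove the point: 8 of 137 counts disorders, not patients, and the galactosylation defects are described as one of the largest subgroups.

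Second, the generic factor models could carry treatment. They could, so the plan does not prevent separation. But nothing commits to it, the time-varying version is optional, and a time-constant term would misclassify patients who start therapy during follow-up.

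Third, a pooled slope over all types would be a poor comparator for a type-specific therapy in any case, and no passage commits to using it as an external control. That is fair, and it supports reporting by type.

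Fourth, Aim 1 does not specify untreated disease, and restricting to untreated visits selects a possibly milder group. Both are true, which is why neither trend should stand alone.

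Finally, a reader might infer that therapy is not recorded. That cannot be judged: Study Activities refers to a list of retrospective data attached to the application, which is not among the documents.

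**Conclusion.** The point holds for the treatable types. Followed as written, the trend model blends treated and untreated visits, and for those types the result is a compromised reference for the purpose that the Background gives.

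It would be tempting to conclude that the study cannot provide a benchmark at all. The documents do not support that: a trend in PMM2-CDG alone, at least a third of the cohort, is not affected by the listed therapies, although the plan does not specify trends by type.

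Nor do the documents support a specific bias. The range of about 1% to 39% for the pooled slope, and the 20% to 75% within a type, are arithmetic on assumed inputs. They require constant treatment status and a common untreated slope. Size and direction remain unknown. This is a cheap improvement to the analysis plan, not a flaw that invalidates the study.

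**What to change.** - Confirm that start and stop dates of CDG-directed therapy and of interventional-trial participation are captured; add the fields if they are not.
- In the Data Analysis Plan, name treatment status as a time-varying term with its own age slope, or split each patient's visits at the start of therapy.
- Report the age trend by CDG type, at least PMM2-CDG versus treatable types, for untreated and treated visits separately, with the all-visits trend alongside.
- For treatable types, label the all-visits trend as the course under current care.
- Use pre-enrolment data for the untreated period only where the measure exists in the records. The rating scale and PROMIS are completed at study visits, so earlier scores cannot be presumed.

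The cost is analysis-plan wording and, if the dates are not already collected, a few data fields. The statistical price is wider intervals in small treatable types, with at most about five annual visits per patient. Confounding by severity at the start of therapy also remains possible, which is why both trends are shown. No change to anyone's treatment is proposed.

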A list of retrospective data to be collected from the medical record is attached to the application. Optional blood, stool, and urine samples will be collected for research at each annual visit (once per year over the course of 5 years of follow up). If a participant is unable to provide urine, stool, or blood samples due to age or other logistical difficulty, we will forego research sample collection and rely purely on clinical/research data collected over the course of the study. If any clinical residual samples (urine, blood, or stool) are available for these participants unable to provide fresh research collections, we may use these instead. These clinical residuals would come from the Biochemical Genetics Lab (BGL) at Mayo or from participating sites' laboratories, if any sample remains. Skin biopsies will be only taken for diagnostic purposes. Leftover tissue material from clinical diagnostics will be used for biomarker discovery. If a subject doesn't complete regular follow up appointments, we will reach out to them via phone or email to obtain follow up information and complete questionnaires to ensure we are able to obtain accurate follow up information. Participants will be offered up to \$700 reimbursement to cover lodging and travel expenses, per visit at all sites except for the University of Minnesota Masonic Children's Hospital. University of Minnesota will offer \$75 per visit to each participant as remuneration and will not offer travel reimbursement.

Accrual:

Our goal is to enroll 150 patients of all ages and from all CDG types over 5 years in the natural history study. At least 50 of the 150 enrolled subjects will have a diagnosis of PMM2-CDG. There will be no exclusion based on sex, ethnicity or socio-economic status. The sample size of 100 was based on a count of the number of affected individuals currently clinically followed and current patient census taken by CDG CARE in August of 2018.

Participating Sites:

We will collaborate with other sites on this study with Mayo Clinic acting as the IRB of record. The target accrual in total will remain at 150 participants. The sites below will be included in the study:

1. Children's Hospital of Pittsburgh at University of Pittsburgh Medical Center – PI is [name]
2. Seattle Children's Hospital – PI is [name]
3. Tulane University Medical School – PI is [name]
4. Baylor College of Medicine – PI is [name]
5. University of Minnesota Masonic Children's Hospital – PI is [name]

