Examples

- The study plans to conduct a retrospective chart review and ask subjects to complete a questionnaire.
- The study plans to include subjects previously diagnosed with a specific disease and add newly diagnosed subjects in the future.

The study will use data that have been collected under another IRB protocol. Include in the Methods section and enter the IRB number from which the research material will be obtained. *When appropriate, note when subjects have provided consent for future use of their data and/or specimens as described in this protocol.*

Enter one IRB number per line, add more lines as needed

Data Specimens Data & Specimens _____

Data Specimens Data & Specimens _____

Data Specimens Data & Specimens _____

Data Analysis

Data Analysis Plan: The study will be used to estimate the prevalence and distribution of scores and the precision of these estimates based on the specified sample size was assessed. For a binary variable (e.g. likelihood of moderate or severe for a given component of the severity score) the expected size of the confidence interval is a function of the sample size and true underlying prevalence.

The extensive clinical and laboratory data collected in this study will be recorded on electronic forms at each site and submitted to DMCC. Almost all of the clinical exams and laboratory studies will provide either a numerical score or categorical score for phenotypic severity, thereby allowing statistical analysis looking for longitudinal changes and exploring potential biomarkers that correlate with disease. We will utilize the statistical expertise of the DMCC for data analysis. The DMCC database will also be able to house imaging studies and genomic data collected from medical records in a de-identified way.

Clinical and laboratory measures, as well as demographics and age of onset, will be summarized using descriptive statistics. Principal component analysis (PCA) will be applied to summarize multivariate measurements. Baseline association between two factors of interest will be assessed using a general linear regression for a continuous response variable and logistic regression for a categorized response variable, after adjusting for potential confounders.

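### Affected siblings are eligible, but no planned model or interval has a family level; if siblings enrol, some intervals will be modestly too narrow

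*Combined protocol and SAP*

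**What the plan says.** The Background defines the disease as inherited: "A congenital disorder of glycosylation is a monogenic disorder". The Inclusion Criteria invite "All individuals with a genetically, enzymatically, or molecularly confirmed diagnosis of CDG or NGLY1 deficiency", and also probable cases awaiting confirmation. The next line reads "Exclusion Criteria: none". No sentence limits enrolment to one patient per family, so an affected brother or sister of an enrolled patient is eligible.

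Under Accrual, "Our goal is to enroll 150 patients of all ages and from all CDG types over 5 years", and "At least 50 of the 150 enrolled subjects will have a diagnosis of PMM2-CDG". At most 100 places are therefore left for all other types together.

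The Data Analysis Plan then sets out:

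- **Prevalence intervals:** "the expected size of the confidence interval is a function of the sample size and true underlying prevalence". Nothing else enters the width.
- **Baseline associations:** linear and logistic regression with confounder adjustment, and no cluster term or robust variance.
- **Longitudinal models:** "the average trend with age will be estimated using mixed effects models to account for the correlation of repeated measures from a subject". The random effects are an intercept and slope for the subject. The model for change in patient-reported outcomes has a participant-level intercept only.
- **PLS:** no resampling unit is stated.

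No analysis step provides for relatedness between patients.

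**The concern.** Siblings with the same monogenic disorder would usually share the causal genotype, and they commonly share a home. Their patient-reported outcomes may also share a respondent, since Study Activities lets the patient or family complete them. Two siblings then carry less information about a prevalence or a mean than two unrelated patients do. A subject-level random effect cannot absorb this, because the dependence lies between subjects.

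Aim 1 is to describe prevalence and severity across CDG types, and the Background presents natural history as the yardstick for judging later therapies. Intervals that overstate precision would carry into that use. The data will also be archived in de-identified form for outside researchers. If family linkage is lost at that step, later users cannot correct for it.

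**Working it through.** **No plan figure to reproduce.** The documents state no interval width, confidence level, power or alpha. The sample size rests on a head count ("The sample size of 100 was based on a count of the number of affected individuals currently clinically followed"; the same section sets a target of 150, which is a separate inconsistency). The baseline below is therefore the interval that the plan describes, with an assumed 95% level.

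**Inputs**

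- From the documents: n = 150 overall; n = 50 as the PMM2-CDG minimum.
- Assumed: *s*, the share of patients enrolled as one of a sibling pair (5-20% for the pooled cohort); *ρ*, the within-family correlation (0.3-0.8); prevalence p = 0.5; a type with 6 patients as an example of a small group.

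**Independent half-width:** 1.96 × √(p(1−p)/n)

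- n = 150: 1.96 × 0.5/√150 = 8.0 percentage points
- n = 50: 13.9 points
- n = 6: 40.0 points

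**Design effect.** In general DEFF = 1 + (Σn_f²/N − 1)ρ, where n_f is the number of patients in family f. With pairs and singletons, Σn_f² = 4(sN/2) + (1−s)N = N(1+s), so DEFF = 1 + sρ. The correct width is the independent width times √DEFF. True coverage of the nominal 95% interval is 2Φ(1.96/√DEFF) − 1.

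| Group | s | DEFF, ρ = 0.3 to 0.8 | Correct interval wider by | Half-width (points) | True coverage |
|---|---|---|---|---|---|
| n = 150 | 0 | 1.00 | 0% | 8.0 | 95.0% |
| n = 150 | 5% | 1.015-1.04 | 0.7-2.0% | 8.1-8.2 | 94.8-94.5% |
| n = 150 | 10% | 1.03-1.08 | 1.5-3.9% | 8.1-8.3 | 94.7-94.1% |
| n = 150 | 20% | 1.06-1.16 | 3.0-7.7% | 8.2-8.6 | 94.3-93.1% |
| n = 50 | 20% | 1.06-1.16 | 3.0-7.7% | 14.3-14.9 | 94.3-93.1% |
| n = 6, 2 pairs | 67% | 1.20-1.53 | 9.5-23.8% | 43.8-49.5 | 92.6-88.7% |

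At n = 150 and s = 20%, the effective sample size is 150/1.06 = 142 down to 150/1.16 = 129.

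The n = 150 and n = 50 rows at s = 20% have the same relative error. Small n alone does not make it worse; a larger share in pairs does. One pair is 2/150 = 1.3% of the cohort but 2/6 = 33% of a six-patient type. At n = 6 the normal approximation is poor even without siblings, so the coverage in that row is only a guide.

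**Planned mixed model.** The model-based standard error was compared with the true one when siblings share part of the random intercept and slope. This assumed 5 annual visits, sibling ages 1.5 to 5 years apart, assumed variance components, 15 pairs among 150, and ρ = 0.5 to 0.8.

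- Intercept: true standard error 4.6-7.2% larger
- Time-constant factor shared by siblings: 4.4-7.0% larger
- Age slope: 2.6-3.9% larger

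**The case against.** The strongest reply is that this is a conditional risk of modest size. The documents make siblings eligible, but they do not say that any will enrol, and they give no inheritance pattern, sibling count or correlation. The Background also describes wide clinical variation within subtypes. Part of the resemblance between siblings in the pooled cohort is simply that they share a CDG type, and that part disappears within a type or after adjustment for type. The correlations used here could therefore be too high for type-specific estimates. All of this stands, and it is why the size is given as a range that starts from zero.

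Three stronger readings are tempting and are not supported:

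- *The intervals are too narrow.* A reader might take this as established. It holds only if siblings enrol and resemble each other.
- *The problem is worst in rare types.* At the same sibling share the relative error is the same at any n. No document shows a higher share in rare types.
- *All p-values are too favourable.* For a regression coefficient the inflation is roughly 1 + sρ_yρ_x, where ρ_y and ρ_x are the sibling correlations of the outcome and the factor. It vanishes when the factor is unrelated between siblings, and standard errors can even be too large when the factor differs between them.

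It can also be said that the retrospective data list attached to the application, which is not in these documents, may already hold a family identifier, and that the coordinating centre's statisticians may handle relatedness. Either is possible, so the absence of the identifier cannot be asserted. Neither puts a family level into the models as written.

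**Conclusion.** The plan makes siblings eligible and specifies no family-level dependence in any model or interval. Followed as written, it understates uncertainty for prevalences, means and sibling-shared factors whenever affected siblings enrol and resemble each other.

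On the assumed values, the pooled effect is modest: intervals that should be about 1-8% wider at n = 150, and an age-slope standard error about 3-4% too small when 20% are in pairs. It can reach about 10-24% in a small type where pairs are a large share, as in the example of 2 pairs among 6 patients. With no siblings it is nil. No figure stated in the plan is wrong on this account. The point is an inexpensive improvement, best made while family linkage can still be recorded.

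**What to change.** - Record a family identifier at enrolment, or confirm that one is already collected, and carry a coded version into the de-identified archive.
- Use family-clustered standard errors or a family random intercept in the baseline regressions, prevalence intervals and mixed models. For the age slope, clustered standard errors are the safer choice, because a family intercept alone does not absorb a rate of change that siblings share.
- Resample or cross-validate by family in the PLS analysis.
- Report the number of families beside the number of patients for each CDG type. Where a type has too few families for a clustered variance to be reliable, add a sensitivity analysis with one patient per family.

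The cost is one data field, a variance option in the analysis code and slightly wider intervals. If no siblings enrol, the family level has nothing to adjust for.
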